9.3.5 Neurological examination

A standard neurological examination will be performed. Clinically significant new or worsened abnormalities in the neurological examination must be reported as AEs.

9.3.6 Psychiatric and mental status

Psychiatric and mental status will be reported by recording the presence or absence of psychiatric symptoms, mental impairment, and behavioral problems. Clinically significant new or worsened abnormalities must be reported as AEs.

9.3.7 Assessment of suicidality

Suicidality will be assessed by trained study personnel using the C-SSRS for subjects ≥ 6 years of age. This scale will be used for screening as well as to assess suicidal ideation and behavior that may occur during the study. The C-SSRS will be completed according to the tabular schedules of study procedures, Section 5.2.

The “Since Last Visit” version of the C-SSRS will be used, with the following exceptions:

- For directly enrolled subjects, the “Baseline/Screening” version of the C-SSRS should be completed at the ScrV.

If a subject turns 6 years of age during the study, the “Already Enrolled” version of the C-SSRS should be completed at the first visit after the sixth birthday.

The C-SSRS is not validated for subjects < 6 years of age and will not be used for this population. Subjects should be monitored for any changes in mood, ideas, or behavior for warning signs of depression. The Investigator should be aware of common warning signs that might be a signal for risk of depression. For common signs and symptoms of depression in children younger than 6 years old, reference should be made to the current version of the Diagnostic and Statistical Manual of Mental Disorders. Parents and caregivers should also be advised accordingly and effort should be made at clinic visits to specifically assess potential depression.

9.3.8 BRIEF-P and BRIEF

The BRIEF-P and the BRIEF are validated tools that will be used for the evaluation of subjects ≥ 2 years to < 5 years of age and ≥ 5 years of age, respectively. The BRIEF-P and BRIEF include rating forms used by parents to assess subjects’ executive functioning. Executive functions broadly encompass a set of cognitive skills that are responsible for the planning, initiation, sequencing, and monitoring of complex goal-directed behavior.

The BRIEF-P rating form consists of items that measure various aspects of executive functioning: Inhibit, Shift, Emotional Control, Working Memory, and Plan/Organize. The clinical scales form 3 broad indexes (Inhibitory Self-Control, Flexibility, and Emergent Metacognition) and 1 composite score (Global Executive Composite).

The BRIEF rating form contains items in nonoverlapping clinical scales. These theoretically and statistically derived scales form 2 broader Indexes: Behavioral Regulation (3 scales) and Metacognition (5 scales), as well as a Global Executive Composite score.

Both the BRIEF-P and the BRIEF include validity scales to measure negativity and inconsistency of responses.

10 ASSESSMENT OF EFFICACY

Efficacy variables will be assessed using the seizure count information recorded on the DRC and EEG data. Seizure count information will be evaluated over the Evaluation Period by 3-month

periods based on the DRC (EV until EDV or FV). For directly enrolled subjects, seizure count information collected during the Up-Titration Period will be summarized separately. The EEG data will be reviewed at 6 months and yearly thereafter.

10.1 Efficacy assessments for seizure data based on DRC

At each visit, the subject/parent(s)/legal representative(s) will receive a DRC, which has to be filled in daily by the parent(s)/legal representative(s) or subject, if applicable, and returned at the next visit. No DRC will be dispensed at the SV or the FV.

The date and the number of epileptic seizures will be recorded on the DRC, as well as the type of seizure (according to individual description of seizures), occurrence of clusters, intake of concomitant AEDs, undesirable events with start and end dates, health care provider consultations not foreseen per protocol, and changes in concomitant medication, if applicable.

The written information will be discussed with the subject/parent(s)/legal representative(s) at each visit in order to ensure completeness and accuracy. As a result of the discussion, the Investigator will assess the seizures according to the ILAE codes and record the seizure types and frequency on the eCRF; he/she will also confirm the presence of AEs (if applicable). Concomitant medication changes, health care provider consultations not foreseen per protocol, and AEs will be reported by the Investigator on the specific pages of the eCRF.

The DRC will be considered as source documentation. The subject/parent(s)/legal representative(s) should be educated to complete the DRC on a daily basis (eg, when taking evening dose of BRV). Substantial noncompliance with diary completion (seizures recording) may result in subject discontinuation from the study at any time by the Investigator or the Sponsor.

10.2 Efficacy assessments for seizure data based on EEG

All EEGs specific to this study will be recorded in the eCRF modules specifically designed for this purpose.

10.3 Other assessments

Other assessments will be performed at the visits indicated in [Table 5–1](#), [Table 5–2](#), and [Table 5–3](#).

10.3.1 Direct cost parameters

Direct cost parameters include the following: concomitant medications, medical procedures, health care provider consultations not foreseen by the protocol, and hospital stays.

10.3.1.1 Concomitant medications/treatments

Concomitant medication information will be collected and recorded.

For LTFU subjects, any ongoing medications (including AEDs and non-AEDs) at the time the subject completed the core study should not be recorded in the N01266 eCRF. Changes in ongoing concomitant medications should be recorded in the N01266 eCRF. In this event, the medication should be recorded in the eCRF for N01266 with the start date corresponding to the date of change in administration.

Details of the concomitant medications and therapy are provided in Section 7.8.

10.3.1.2 Medical procedures

Data on medical procedures (surgery, therapeutic and/or diagnostic, hospitalizations) undertaken during the study will be collected and recorded in the eCRF. Electrocardiograms specific to this study will not be recorded on the medical procedures page of the eCRF, but in the modules specifically designed for this purpose.

10.3.1.3 Health care provider consultations not foreseen by the protocol

Data collected for health care provider consultations not foreseen by the protocol will include the type of provider (general practitioner, specialist physician, nurse), the site of care (office-private, office-hospital, home, emergency room), and the reason leading to the consultation.

10.3.1.4 Hospital stays

Data collected for hospital stays will include the reason leading to the hospitalization, the admission ward, transfers, and length of stay.

10.3.2 Bayley Scales of Infant and Toddler Development, Third Edition

The Bayley-III scales are validated as a tool for assessment of neurological development in young children and recognized internationally as one of the most comprehensive developmental assessment instruments (Sattler and Hoge, 2006) used to examine the major facets of a young child's development (Bayley, 2006). The Bayley Scales of Infant and Toddler Development, Third Edition (Bayley-III) are a standardized individually administered adaptive assessment that measures the developmental functioning of infants and young children from 1 month to 42 months of age (Bayley, 2006). The Bayley-III scales measure cognitive, language, motor, social-emotional, and adaptive development and are a revision of the predecessor, the Bayley Scales of Infant Development, Second Edition (BSID-II) (Bayley, 1993). The Bayley-III scales are a technically sound instrument, with strong internal consistency, as well as test-retest stability. The Bayley-III scales are provided in English and in countries where a validated translation is available.

The Bayley-III scales are an individually administered adaptive assessment that presents children with situations and tasks designed to produce an observable set of behavioral responses. They consist of a cognitive scale, a language composite scale with receptive and expressive language subscales, and a motor composite scale with fine and gross motor subscales to be completed by the Investigator or designee, and of a social-emotional scale, comprising social-emotional competence and sensory processing, and an adaptive behavior scale, which assesses the attainment of skills necessary for the development of independence, to be completed by the child's parent or caregiver.

The completion of the Bayley-III scales will require approximately 50 minutes for children who are 12 months old or younger and 90 minutes for children aged 13 months and older.

The Bayley-III scales will be applied to subjects as described in Table 5-1 and Table 5-2. The Bayley-III scale is not applicable to directly enrolled subjects due the age of these subjects (≥ 4 years of age) at entry into N01266.

10.3.3 Achenbach Child Behavior Checklist

The Achenbach CBCL is a widely used validated questionnaire to evaluate a child's competencies and behavioral/emotional problems. Behavioral problems will be scored by the parent(s) or legal representative(s). Depending on the subject's age, 2 versions of the Achenbach CBCL will be used. The Achenbach CBCL/1½-5 checklist is intended for use in children aged between 18 months and 5 years and 11 months. For subjects between 6 years and <16 years, the Achenbach CBCL/6-18 version will be used. The Achenbach CBCL will not be applied to children below 18 months of age.

The Achenbach CBCL should be completed by the same parent(s)/legal representative(s) who completed the CBCL in the core study, when possible. The completion of the Achenbach CBCL will require approximately 45 minutes.

In both questionnaires, the occurrence of certain problems and behaviors in the past 6 months will be scored on the following scale:

0=not true (as far as known)

1=somewhat or sometimes true

2=very true or often true

Eight syndrome scores will be calculated from these questions, which will in turn be summarized by 2 composite scores. Additionally, for each score on the question, syndrome, and total level, categorizations based on a normative sample will be used to evaluate normal, borderline, or clinically relevant behavior.

In addition, the Achenbach CBCL/6-18 includes ratings related to performance in school, activities in leisure time, and special interests.

The version of the Achenbach CBCL appropriate to each subject's age should be administered with the following exception: If a subject completed the Achenbach CBCL/1½-5 at the Baseline assessment and turns 6 years of age between that assessment and the initial YEV, the CBCL/1½-5 should be completed through and including the initial YEV, and subsequently the CBCL/6-18 should be completed.

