- Direct cost parameters: concomitant medications, medical procedures, health care provider consultations not foreseen by the protocol, and hospital stays
- Change from Baseline in the Achenbach CBCL score: the Achenbach CBCL/1½-5 for children from 1½ to 5 years old and the Achenbach CBCL/6-18 for children 6 years and older (age at initiation of study drug in N01266 or core study)
- Change from Baseline in the BRIEF-P/BRIEF score for subjects ≥ 2 years of age (age at initiation of study drug in N01266 or core study)

- Change from the Baseline in the Bayley-III scales for children <18 months of age at baseline of the core study (applicable only to LTFU subjects enrolled in English-speaking countries and in countries where a validated translation is available)
- Change from Baseline in PedsQL for subjects ≥ 2 years of age (age at initiation of study drug in N01266 or core study)

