5.3 Visit sequence

Study visits are to be scheduled in the order presented in the following table:

Table 5–4: Visit sequence

Directly enrolled subjects		
	Visit	Type of visit
	ScrV	Screening
W1	TV1 ^a	TV
W2	TV2 ^a	TV
W3	TV3 ^a	TV
All subjects		
First year follow-up		
M0	V1	EV ^b
M1	V2	MEV
M2	V3	FEV
M3	V4	MEV ^c
M4	-	-
M5	-	-
M6	V5	FEV
M7	-	-
M8	-	-
M9	V6	MEV ^c
M10	-	-
M11	-	-
Second and subsequent years follow-up^d		
M12	V7	YEV
M15	V8	MEV

Table 5–4: Visit sequence

M18	V9	FEV
M21	V10	MEV
and every 3 months thereafter	V11, V12, etc	YEV, MEV, etc

BRV=brivaracetam; EV=Entry Visit; FEV=Full Evaluation Visit; LTFU=long-term follow-up; M=Month; MEV=Minimal Evaluation Visit; ScrV=Screening Visit; TV=Titration Visit; V=Visit; W=Week; YEV=Yearly Evaluation Visit

Note: Visits at W1, W2, W3, and M0 will occur 7 ± 2 days after the previous visit; visits at M1, M2, and M3 will occur 30 ± 7 days after the previous visit; visits at M6, M9, M12, M15, M18, M21, and every 3 months thereafter will occur 90 ± 15 days after the previous visit.

“-” denotes that no visit is scheduled in that month.

^a All directly enrolled subjects must participate in at least TV1, but may participate in fewer than 3 TVs as described in Section 7.2.1.

^b For directly enrolled subjects, the EV represents the point of entry into the Evaluation Period.

^c Hepatic monitoring tests only will be performed as described in Section 9.2.1.

^d Subsequent years will follow the same visit schedule.

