8.1 Screening Visit for directly enrolled subjects only

The ScrV is applicable only to directly enrolled subjects (ie, subjects ≥ 4 years to <17 years of age with POS who have not participated in a core study). The Screening Period will serve as the Baseline Period for directly enrolled subjects. The ScrV is not applicable for LTFU subjects; the first N01266 visit for LTFU subjects is the Entry Visit (Section 8.3.1).

The ScrV assessments will be conducted 7 ± 2 days prior to the first administration of BRV. It is acceptable for the ScrV assessments to be conducted on more than 1 day.

The ScrV assessments are as follows:

- Signing and dating of written Informed Consent by parent(s)/legal representative(s)
- Signing and dating of Assent form by the subject (if applicable, according to age and local requirements)
- Subject identification card dispensing
- Demographic data
- Childbearing potential

- Verification of inclusion/exclusion criteria
- Physical (including Tanner Scale, as applicable) and neurological examinations
- Psychiatric and mental status
- General medical and procedures history
- Epilepsy and AED history
- Vital signs (blood pressure, pulse rate, and body temperature)
- Body weight, height, and head circumference
- ECG
- EEG (A previous EEG documenting the POS diagnosis must be available at the ScrV for directly enrolled subjects. If an EEG is not available at the ScrV, it must be scheduled during the Screening Period.)
- Neuro-imaging procedure (brain magnetic resonance imaging/brain computerized tomography scan [except in Germany]/ultrasounds or any other imaging test) should be performed if no report is available within the previous 2 years
- DRC dispensed
- Recording of medications
- Recording of procedures
- Recording of AEs
- IVRS call
- Laboratory assessments for safety including:
 - Hematology
 - Biochemistry including hepatic monitoring
 - Urinalysis (for subjects for whom sample collection is feasible)
 - Endocrinology
 - Urine pregnancy test (see Section 9.2.1)
- Phenytoin plasma concentrations (if applicable)
- Suicidality assessment (C-SSRS-Baseline/Screening) (for subjects ≥ 6 years of age)
- Achenbach CBCL (version consistent with age at the visit)
- BRIEF-P (<5 years of age)/BRIEF (≥ 5 years of age) (version consistent with age at the visit)
- PedsQL (version consistent with age at the visit)
- Appointment for the next visit (TV1) 7 ± 2 days later

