8.2 Titration Visit(s) (TV1, TV2, and TV3) for directly enrolled subjects only

Directly enrolled subjects will initiate treatment with BRV at TV1 (see Section 7.2.1 for dosing information). The TVs are not applicable for LTFU subjects; the first visit in N01266 for these subjects is the EV (Section 8.3.1).

The first dose of BRV at each titration level will be administered at the clinic during the TV. Subjects will remain on the BRV dose administered at the clinic for 7 ± 2 days before titrating up to the next dose. The BRV up-titration schedule is provided in Section 7.2.1.

A total of up to 3 TVs may be required; however, based on tolerability and seizure control, a subject's BRV dose may be titrated to a lower dose level and 3 TVs would not be needed.

The following assessments are required at each TV:

- Verification of inclusion/exclusion criteria (TV1 only)
- Vital signs (blood pressure, pulse rate, and body temperature)
- Body weight
- ECG
- DRC dispensed
- DRC retrieved
- Seizure count
- Recording of medications
- Recording of procedures
- Recording of AEs
- IVRS call
- Hepatic monitoring of ALT, AST, ALP, total bilirubin, and GGT (TV3 only unless the Investigator anticipates that TV2 will be the final TV, in which case hepatic monitoring assessments are to be done at TV2)
- Study drug dispensed
- Study drug returned (TV2 and TV3 only)
- Study drug compliance (TV2 and TV3 only)
- Suicidality assessment (C-SSRS) (for subjects ≥ 6 years of age)
- Healthcare provider consultation not foreseen by the protocol
- Hospital stays
- Appointment for the next visit 7 ± 2 days later

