8.5 Full Evaluation Visit (all subjects)

- Childbearing potential
- Physical examination
- Neurological examination
- Psychiatric and mental status
- Vital signs (blood pressure, pulse rate, and body temperature)
- Body weight, height, and head circumference
- EEG (for LTFU subjects only)
 - For subjects ≥ 2 years of age at V5 who have typical absence seizures, an EEG of at least 1 hour that includes hyperventilation and intermittent photic stimulation must be performed only at V5 and yearly thereafter.
 - For subjects < 2 years of age at V5, an EEG of at least 24 hours of recording must be performed at V5 and yearly thereafter.
- DRC dispensed
- DRC retrieved
- Seizure count
- Assessment of seizure types for subjects < 2 years of age
- Recording of medications
- Recording of procedures
- Recording of AEs
- Suicidality assessment (C-SSRS) (for subjects ≥ 6 years of age)
- IVRS call
- Study drug dispensed
- Study drug returned

- Study drug compliance
- Laboratory assessments for safety
 - Hematology
 - Biochemistry (including hepatic monitoring of ALT, AST, ALP, total bilirubin, and GGT)
 - Urinalysis (for subjects for whom sample collection is feasible)
 - Urine pregnancy test (see Section 9.2.1)
- BRV plasma concentrations
- Phenytoin plasma concentrations (if applicable)
- Bayley-III scales (for LTFU subjects enrolled in English-speaking countries and in countries where a validated translation is available, <18 months of age at baseline of the core study, and <42 months of age)
- Achenbach CBCL (see Section 10.3.3)
- BRIEF-P (≥ 2 years to <5 years of age)/BRIEF (≥ 5 years of age) (see Section 9.3.8)
- PedsQL (see Section 10.3.5)
- Health care provider consultations not foreseen by the protocol
- Hospital stays
- Appointment for the next visit according to the schedule described in Section 5.3

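### In directly enrolled subjects, the Month 2 CBCL rates a 6-month window that is nominally 56–63% pre-BRV, so its change from Baseline is not an on-treatment change

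*Protocol*

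**What the plan says.** Section 10.3.3 sets the same recall period for the CBCL/1½-5 and the CBCL/6-18: "In both questionnaires, the occurrence of certain problems and behaviors in the past 6 months will be scored on the following scale". Each item is scored 0, 1 or 2 according to how true or how frequent the behavior is.

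Table 5-2 and Section 8.5 list the CBCL at the Full Evaluation Visit (FEV) without restricting it to a particular FEV. The CBCL footnote in Table 5-2 deals only with which age version to use. Table 5-4 places FEVs at V3 (Month 2) and V5 (Month 6) in the first year.

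For directly enrolled subjects, Section 8.1 has the CBCL completed at the Screening Visit (ScrV), 7 ± 2 days before the first BRV dose, and states: "The Screening Period will serve as the Baseline Period for directly enrolled subjects". Section 8.2 adds: "Directly enrolled subjects will initiate treatment with BRV at TV1". Section 4.3 names the variable, "Change from Baseline in the Achenbach CBCL score", and Section 12.5 plans a descriptive analysis, with ScrV as Baseline for these subjects.

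**The concern.** One of the other objectives in Section 3.3 is to assess the effect of BRV on behavior with the CBCL. A change from Baseline serves that objective only if the post-Baseline rating describes behavior on BRV. At Month 2, the 6-month recall reaches back past the first dose and past the ScrV rating. The two scores being subtracted then describe largely the same days.

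The practical risk is a V3 summary close to zero that is read as early behavioral reassurance, when the rating has had limited opportunity to register a change. At least 100 directly enrolled subjects are planned among about 600.

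**Working it through.** The protocol gives no figure of its own to reproduce, so this is calendar arithmetic from the visit rules.

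**Inputs**
- Recall window: 6 months, taken as 365.25 / 2 = 182.6 days (Section 10.3.3).
- Spacing of titration visits and Entry Visit (EV): "Visits at W1, W2, W3, and M0 will occur 7 ± 2 days after the previous visit" (Section 5.3).
- Number of titration visits, k: "All directly enrolled subjects must participate in at least TV1, but may participate in fewer than 3 TVs" (Section 5.3), so k = 1, 2 or 3.
- Spacing from EV to V3: "visits at M1, M2, and M3 will occur 30 ± 7 days after the previous visit" (Section 5.3), so two intervals of 30 ± 7 days.
- ScrV is 7 ± 2 days before the first dose (Section 8.1).

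**Formulas**
- Days on BRV at V3: d = k × 7 + 2 × 30
- Pre-BRV share = (182.6 − d) / 182.6
- Share already rated at ScrV = (182.6 − d − 7) / 182.6

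**Nominal schedule at V3**

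| Titration visits | Days on BRV | Pre-BRV days (share) | Already rated at ScrV (share) |
|---|---|---|---|
| 1 | 7 + 60 = 67 | 115.6 (63%) | 108.6 (60%) |
| 2 | 14 + 60 = 74 | 108.6 (59%) | 101.6 (56%) |
| 3 | 21 + 60 = 81 | 101.6 (56%) | 94.6 (52%) |

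A 180-day window gives pre-BRV shares of 63%, 59% and 55%.

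**Extremes of the permitted visit windows at V3**
- Earliest, one titration visit: 5 + 2 × 23 = 51 days on BRV; (182.6 − 51) / 182.6 = 72% pre-BRV.
- Latest, three titration visits: 3 × 9 + 2 × 37 = 101 days on BRV; (182.6 − 101) / 182.6 = 45% pre-BRV.
- Latest, with titration capped at 3 weeks: 21 + 74 = 95 days on BRV; 48% pre-BRV.

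If each visit interval is assumed uniform over its permitted days, a simulation puts the pre-BRV share above half in 100%, more than 99.9% and about 94% of subjects with 1, 2 and 3 titration visits.

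**V5 (Month 6)**
- This adds one 30 ± 7 day interval and one 90 ± 15 day interval, so the nominal exposure is k × 7 + 3 × 30 + 90 = 187, 194 or 201 days. The pre-BRV share is 0%.
- With every visit at its earliest day, exposure is 5k + 3 × 23 + 75 = 149, 154 or 159 days. The pre-BRV share is then 18%, 16% or 13%.

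**Early Discontinuation Visit (EDV)**
- Half the window is 91.3 days. BRV covers more than half of it from EV + 84 days (91.3 − 7) with one titration visit, or EV + 70 days (91.3 − 21) with three.
- At EV + 150 days, BRV covers 157 / 182.6 = 86% to 171 / 182.6 = 94% of the window.

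**The case against.** The strongest case against is one of weight. The CBCL is an other variable, analyzed descriptively, with no test or decision attached. The study is planned for at least 3 years, subject to earlier stopping conditions, and every CBCL from Month 6 onward has a window essentially all on BRV. How V3 scores are summarized could be settled in the SAP, which was not available here. All of this stands and keeps the point minor. It does not remove the point: the recall period and the visit schedule are both fixed in the protocol, and no analysis rule can turn a mostly pre-treatment rating into an on-treatment one.

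Four stronger readings are tempting, and the documents do not support them.

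- **That V3 shows only 37–44% of the true effect** (67 / 182.6 to 81 / 182.6). This needs every day in the window to count equally and an effect that is constant from the first dose. The items are scored on a three-level occurrence scale, not as a daily average, and parents may weight recent behavior more. A behavior that first appears on BRV can move an item from 0 to 1 or 2, so carry-over more plausibly masks improvement than new worsening.
- **That any EDV in the first 6 months is equally affected.** The working shows that BRV already covers most of the window before the nominal Month 3 visit, and 86–94% of it at EV + 150 days.
- **That subjects from EP0065 share the problem.** They first complete the CBCL at the EV, but they received BRV in EP0065 for a time this protocol does not state, so their pre-BRV share is unknown.
- **That the CBCL change from Baseline is diluted throughout the study.** Only V3 and early EDV scores are affected.

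**Conclusion.** The point holds for directly enrolled subjects at V3. On the nominal schedule, 56–63% of the rated window precedes BRV for every permitted number of titration visits, and 52–60% repeats days already rated at ScrV. Over all permitted visit windows the pre-BRV share runs from about 45% to 72%, so more than half is the usual case and not a certainty.

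The overlap rests only on the protocol's recall period and visit intervals. That the V3 change is pulled toward no change is a reasonable inference, but its size cannot be derived from the protocol. No primary or secondary variable is affected. Severity: minor.

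**What to change.** - Add a footnote to the CBCL row of Table 5-2 and matching wording in Section 8.5: for directly enrolled subjects, the first post-Baseline CBCL is at V5 (Month 6). The protocol already restricts other assessments to named visits, such as EEG from V5 and hepatic tests at V4 and V6.
- Where V3 scores already exist, list them and do not summarize them as on-treatment change from Baseline.
- Keep the CBCL at the EDV. Summarize EDV scores with less than 6 months of BRV separately by exposure. Excluding them would remove early leavers from the summaries and add selection.

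The cost is one footnote and one line of text, and it saves a questionnaire of about 45 minutes per directly enrolled subject at V3. The downside is that these subjects have no Month 2 CBCL. BRIEF-P/BRIEF, PedsQL (4-week recall), psychiatric and mental status and AE recording still cover that visit.
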